9.6.4 Pregnancy Testing

Female patients of childbearing potential will have a serum (at Screening) or urine pregnancy test at any other time points specified in the Schedule of Events (Table 1) and in Section 12 STUDY Procedures. Female patients with a positive pregnancy test at Screening do not meet eligibility criteria for enrollment. Additional pregnancy tests will be performed at any visit in which pregnancy status is in question.

Refer to Section 10.4 Pregnancy for details on the reporting procedures to follow in the event of pregnancy.

Page 39

9.6.5 Electrocardiogram (ECG)

A standard 12-lead safety ECG (single tracing) will be recorded with the patient resting comfortably in the supine position at the time points specified in the Schedule of Events (Table 1 Schedule of Events) and in Section 12 STUDY Procedures. The QTc interval should be evaluated. Clinically significant changes from baseline will be recorded as AEs.

9.6.6 Physical Examination

A complete physical examination is to be performed at each clinic visit or, if applicable, at early discontinuation from the study. Complete physical examination will include assessments of general appearance as well as the following:

- Head
- Eyes
- Ears
- Nose
- Throat
- Cardiovascular
- Dermatologic
- Lymphatic
- Respiratory
- Gastrointestinal
- Musculoskeletal

Weight will be measured with each physical examination throughout the study. Height (cm.) will be measured at screening only.

Other body systems may be examined. Clinically significant changes from baseline will be recorded as AEs

9.7 Efficacy Variables

The timing of required evaluation is described in the Schedule of Events in Table 1 Schedule of Events following the sequence listed below.

Assessment	Start Time After Dose (+ 10 minutes unless otherwise specified)
HFSME	45 minutes
6-minute walk test	After HFSME
Time to rise from floor	After 6-minute walk
Time to rise from chair	After rise from floor
Time to climb 4 stairs	After rise from chair
Time to walk 10 meters	After climb stairs
Quality of Life Assessment	After 10-meters walk

9.7.1 Hammersmith Functional Motor Scale Expanded (HFSME)

The HFSME (Appendix 1) assess motor function (e.g. lying, rolling, sitting, crawling, attaining standing, walking, running, and jumping) in order of progressive difficulty, with higher values showing higher function abilities. The HFSME was expanded from the original 20-item Hammersmith functional motor scale by incorporating 13 relevant items to eliminate the "ceiling" effect of the original scale when applied to ambulant SMA patients. Each item scores 2 for unaided, 1 for assistance, and 0 for inability. A total score is calculated by summing the scores of the individual items. The total score can range from 0 (all activities failed) to 66 (all activities achieved unaided). The HFSME shows good test-retest reliability and correlation with other clinical measures in SMA, especially in Type 3 (Montes, 2015).

9.7.2 6-minute walk test

This is a test of endurance which has been validated for ambulant patients with SMA (Montes, 2010). Participants are instructed to walk as fast as possible along a 25-meter linear marked course for 6 minutes. Meters walked are recorded.

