two years of age. SMA Type 2 also presents very early, before 18 months of age, but symptoms are less severe, and these children are able to sit or even to stand unsupported, although they do not achieve the ability to walk independently. SMA Types 3 and 4 are the least severe forms. In Type 3, symptoms appear after 18 months of age, and severity is highly variable. Many patients have only proximal muscle weakness and can stand and walk independently, sometimes until the late disease stages. Life expectancy is near normal. SMA Type 4 has an adult onset, sometimes after 30 years of age, and muscle weakness, mainly of proximal muscles, is relatively mild and slowly progressing, although loss of independent walking has been rarely reported (Shababi 2014).

SMN protein localized in the presynaptic terminals at the neuromuscular junction (NMJ) (Dombert 2014) and its role in NMJ development has been tested by the failure of the cultured muscle cells derived from SMA patients to cluster acetylcholine receptors (AChRs) at the junction (Arnold 2004). In addition, neurofilament accumulation along with poor terminal arborization in postnatal diaphragm samples of SMA Type 1 have been reported (Kariya 2008). Further evidence for a possible role of abnormal NMJ in human SMA pathology derives from a recent study providing a detailed structural characterization of NMJ defects in SMA fetuses (Martinez-Hernandez 2013); main prenatal defects were abnormal modification of acetylcholine receptor clustering, irregular accumulation and positioning of synaptic vesicles, and atypical nerve terminals in motor endplates of SMA Type 1 samples, whereas SMA Type 2 fetuses were similar to controls.

In SMA mice some findings suggest skeletal muscle fiber disruption, such as increased activity of cell death pathways (Mutsaers 2011), abnormal differentiation in muscle satellite cells, deficient formation of myotubes, and decreased muscle fiber size (Lee 2011; Hayhurst 2012). Interestingly, loss of murine SMN specifically in the skeletal muscle causes muscle necrosis, paralysis, and death (Cifuentes-Diaz 2001).

In addition, restoration of SMN in the mature muscle or increasing the muscle mass through different molecules have limited therapeutic benefits in SMA mice (Gavrilina 2008; Rose 2009; Bosch-Marce 2011), further confirming that NMJ maturation defects and abnormal synapses are the hallmark of SMA pathology (Kariya 2008).

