9 INVESTIGATIONAL PLAN

9.1.1 Overall Study Design and Plan

This is a stratified, randomized (1:1), double-blind, placebo-controlled, , 2-treatment, 2-sequence, crossover, outpatient study designed to evaluate the safety, tolerability and efficacy of amifampridine in ambulatory patients diagnosed with SMA Type 3. The study will include about 12 male and female SMA Type 3 patients,

The planned duration of participation for each patient is at least 60 days excluding the screening period, which can last up to 14 days.

All patients who sign an informed consent will be screened for eligibility to participate in the study: inclusion and exclusion criteria; medical and medication history; complete physical exam (including height, weight); vital signs; standard 12-lead ECG, including QTc evaluation; clinical laboratory testing; serum pregnancy testing (females of childbearing potential only; result must be negative to proceed into the run-in period with open-label IP

administration); confirmed molecular diagnosis of SMA; and assessment of serious adverse events (SAEs) (Table1)

Table 1 Schedule of Events) conducted at the start of the Run-in period (Day 1, before starting medication) and during Run-in, until stable dose and frequency of amifampridine is established for at least 7 days, and at least a 3-point improvement in HFMSE score is achieved. Screening and the start of the Run-in period may be combined into a single visit, in which case overlapping procedures/assessments will only need to be performed once. On the last day of the Run-in period (Day 0), procedures/assessments, as detailed in Table 1 will be conducted to confirm eligibility for randomization, including a negative pregnancy test. Every attempt should be made to have the same individual perform all assessments for a patient throughout the study.

Randomized patients will be assigned to one of 2 treatment sequences under double-blind conditions, either placebo or amifampridine phosphate in Part 1, and then cross-over in Part 2 to receive the alternate medication which was not taken in Part 1.

Open-label Run-in

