Amifampridine dose will be titrated upward every 3 to 4 days, starting at 15 mg/day, at the discretion of the Investigator. Patients will either visit or have telephone/video contact with the site for each dose titration and at least one in-person site evaluation at Week 3 of the Runin period. When the Investigator determines that the patient has reached the maximal tolerable and efficacious dose, the patient should demonstrate they can remain on a stable dose and frequency for at least an additional 7 days. The Open-label Run-in period may be extended if additional time is needed for the dose titration. At the end of this period, patients must show at least a 3-point improvement in HFMSE score from start of Run-in, to be eligible for randomization (Day 0).

Randomization

Patients who continue to meet all the inclusion and exclusion criteria will be randomized on the last day of the Run-in period (Day 0).

Period 1 (Days 1-14) (± 1 day for each of Days 7 and 14)

Patients who have successfully completed the Open-label Run-in and continue to meet all inclusion/exclusion criteria will be randomized (1:1 ratio) on Day 0 to receive either

Page 27

amifampridine tablets (10 mg as amifampridine phosphate) or placebo tablets for 14 days, under double-blind conditions, (blinded medication to start after assessments obtained on open-label medication, on Day 0). Test medication will be dispensed by the Catalyst designee, according to the randomization schedule provided by Sponsor. All unused medication and the container must be brought back to the study site at each clinic visit. Safety and efficacy assessments will be made, in the site clinic, on Days 7 and 14 as detailed in the Schedule of Assessments in Table 1 and Section 12 STUDY Procedures.

Period 2 (Days 15-28) (±1 day for each of Days 21 and 28)

Following the in-clinic assessments on Day 14 of Period 1, the Period 1 study medication is collected and the patient should be given the blinded Period 2 medication; either amifampridine phosphate or placebo tablets (whichever they did not receive in Period 1) for 14 days. The Period 2 medication is to start with the next dose after the assessments are performed on Day 14 with Period 1 medication.

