9.2.1 Inclusion Criteria

Individuals eligible to participate in this study must meet all the following inclusion criteria:

- 1. Willing and able to provide written informed consent after the nature of the study has been explained and before the start of any research-related procedures.
- 2. Male or female between the ages of 6 and 50 years.
- 3. Genetically confirmed diagnosis of SMA Type 3.
- 4. Able to walk independently for at least 30 meters (objectively measured at screening).
- 5. Not taking Nusinersen for the treatment of SMA (Nusinersen should be stopped at least 6 months before the screening). Salbutamol is permitted only if the dose has been stable for 6 months before screening.
- 6. Able to swallow oral medication.
- 7. Female patients of childbearing potential must have a negative pregnancy test (serum human chorionic gonadotropin [HCG] at screening); and must practice an effective, reliable contraceptive regimen during the study and for up to 30 days following discontinuation of treatment.
- 8. Ability to participate in the study based on overall health of the patient and disease prognosis, as applicable, in the opinion of the Investigator; and able to comply with all requirements of the protocol, including completion of study questionnaires.

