9.2.2 Exclusion Criteria

Individuals who meet any of the following exclusion criteria are not eligible to participate in the study:

- 1. Epilepsy and currently on medication.
- 2. An electrocardiogram (ECG) within 6 months before starting treatment that shows clinically significant abnormalities, in the opinion of the Investigator.
- 3. Breastfeeding or pregnant at Screening or planning to become pregnant at any time during the study.
- 4. Surgery for scoliosis or joint contractures within the previous 6 months.
- 5. Treatment with an investigational drug (other than amifampridine) or device within 6 months before Screening or while participating in this study.
- 6. Any medical condition that, in the opinion of the Investigator, might interfere with the patient's participation in the study, poses an added risk for the patient, or confound the assessment of the patient.
- 7. History of drug allergy to any pyridine-containing substances or any amifampridine excipient(s).
- 8. Less than 3-point improvement in HFMSE from start to end of Run-in period.
- 9. Uncontrolled asthma.
- 10. Concomitant use with sultopride.
- 11. Concomitant use with medicinal products with a narrow therapeutic window.

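### No upper HFMSE limit at entry: a patient scoring 64, 65 or 66 at the start of Run-in can begin open-label drug although randomization is arithmetically impossible

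*Protocol*

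**What the plan says.** **Scale.** Protocol 9.7.1 describes the HFMSE as "expanded from the original 20-item Hammersmith functional motor scale by incorporating 13 relevant items". On scoring it says: "Each item scores 2 for unaided, 1 for assistance, and 0 for inability". On the total it says: "The total score can range from 0 (all activities failed) to 66 (all activities achieved unaided". The form in Protocol Appendix 1 also ends in a total out of 66.

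**Gain needed.** Protocol 9.1.1 states that "patients must show at least a 3-point improvement in HFMSE score from start of Run-in, to be eligible for randomization (Day 0". Protocol 9.3.3, Protocol 12.2 and the synopsis repeat the rule. Exclusion criterion 8 in Protocol 9.2.2 and SAP 7.2 states it in reverse: "Less than 3-point improvement in HFMSE from start to end of Run-in period".

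**Function at entry.** The only measured functional threshold is inclusion criterion 4: "Able to walk independently for at least 30 meters (objectively measured at screening". That is a lower limit. Neither the synopsis, Protocol 9.2.1 and 9.2.2, nor SAP 7.1 and 7.2 sets an upper limit on HFMSE.

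**When the score is known.** Table 1 schedules HFMSE at Screening and again on Run-in Day 1. Protocol 9.1.1 describes the Table 1 procedures as "conducted at the start of the Run-in period (Day 1, before starting medication) and during Run-in". It also lets Screening and Day 1 be a single visit, with shared procedures done once.

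**The concern.** A bounded scale combined with a required minimum gain implies a highest workable starting score. The plan has both parts but never draws the consequence. A high-functioning ambulatory patient can satisfy every criterion that can be checked before dosing, start titration, and already be certain to fail at Day 0.

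What is at stake is exposure without purpose for that patient. The synopsis gives total treatment as about 8 weeks, and the two blinded periods take 4 of them, so Run-in lasts about 4 weeks and may be extended. Enrolment is open from age 6. Protocol 7.4.3 reports seizures in 10 of 1,454 people exposed to the drug, so the exposure is not free of risk. These patients would also go through titration contacts, the Week 3 visit and the Day 0 assessments.

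**Working it through.** **Inputs**

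- Items: 20 original + 13 added = 33 (Protocol 9.7.1).
- Maximum per item: 2 (Protocol 9.7.1).
- Required gain: at least 3 points, from the start of Run-in to Day 0 (Protocol 9.1.1; exclusion 8 in 9.2.2).
- Upper HFMSE limit at entry: none in either document.

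**Step 1. Reproduce the plan's maximum.** 33 × 2 = 66, which matches the stated figure.

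**Step 2. Largest possible gain.** Largest gain = 66 − score at the start of Run-in. Randomization is possible only if this is 3 or more, so the highest workable starting score is 66 − 3 = 63.

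| Score at start of Run-in | Largest possible gain | 3-point gain possible? |
|---|---|---|
| 62 | 4 | yes |
| 63 | 3 | yes, only with a perfect 66 at Day 0 |
| 64 | 2 | no |
| 65 | 1 | no |
| 66 | 0 | no |

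**Step 3. Which score counts.** The gain is measured from the start of Run-in, not from Screening. A patient at 64 to 66 at Screening who scores 63 or lower on Day 1 could still qualify. If the two visits are combined, one score serves for both.

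**Step 4. Does anything else stop entry?** Inclusion 8 and exclusion 6 leave room for the investigator's judgement, but on overall health, prognosis and medical conditions, not on a motor score. Table 1 marks the eligibility check at Screening and at Day 0, with none on Day 1. Exclusion 8 can be applied only once Run-in is over.

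**Step 5. What the analysis does with these patients.**

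- The FAS and per-protocol sets contain only randomized patients (Protocol 14.2, SAP 10.1), so these patients are in neither.
- They are in the Safety Population, which includes everyone dosed in Run-in (SAP 10.1). Their open-label treatment duration is summarized (SAP 10.10.2).
- The SAP counts an adverse event as treatment-emergent only if it emerges or worsens after randomization. Their Run-in events therefore appear in a listing and not in the TEAE tables (SAP 10.12.1).
- Most safety and efficacy summaries are by sequence (SAP 10.2), and these patients have none.

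**The case against.** **Such patients may be rare or absent.** A score of 64 to 66 means losing at most 2 points, so full marks on at least 31 of 33 items. The added items in Appendix 1 include rising from high kneeling with arms free, a 12-inch two-footed jump, and stairs without a rail. Protocol 7.1 describes proximal weakness in many Type 3 patients, with the legs usually weaker than the arms. Protocol 9.7.1 says the 13 items were added to remove the ceiling seen in ambulant patients. This stands as a reason to expect few cases, but it gives no rate, and a longer scale still stops at 66. Protocol 7.1 also says: "In Type 3, symptoms appear after 18 months of age, and severity is highly variable". High scorers therefore cannot be ruled out.

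**The exposure is not useless.** Safety is a primary objective, and Run-in exposure enters the Safety Population. This stands in part: as shown above, what it adds is a duration summary and listings.

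**A cap at 63 is narrow.** A patient starting at 63 needs a perfect score at Day 0. This is true. The cap removes only certain failures, and for the same reason it costs nothing.

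**Stronger readings that the documents do not support**

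- A reader might infer that these patients distort a Run-in non-response rate. Neither document plans such a rate. Baseline for efficacy is Day 0, and SAP 10.10.1 counts disposition among randomized patients.
- A reader might infer that each one uses up a place in a trial of about 12. The target of about 12 is for patients randomized, and no limit is set on the number entering Run-in.
- A reader might infer bias or loss of power in the primary comparison. Exclusion 8 removes these patients before randomization, so the mixed model sees the same data with or without them.

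**Conclusion.** The gap is real and minor. For starting scores of 64, 65 and 66 the probability of randomization under the written criteria is exactly 0; every score of 63 or below leaves it possible. This rests only on the 66-point maximum, the 3-point rule and the absence of an upper limit, all of which are explicit in the documents.

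The number of patients affected cannot be computed, because neither document gives an HFMSE distribution for ambulatory Type 3 patients. It may be zero. The cost is confined to drug exposure, visits and time for those patients. The treatment contrast, its power and the planned efficacy estimates are untouched. The Safety Population summaries would include these patients, correctly, because they took the drug.

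**What to change.** Add one criterion to Protocol 9.2.1 or 9.2.2, and carry it into the synopsis and SAP section 7: HFMSE total score of 63 or lower at the start of Run-in (Day 1, before the first dose). Tying it to Day 1 uses the same reference score as exclusion 8, so the two criteria cannot disagree, and it still works when Screening and Day 1 are combined. Since Table 1 and SAP Appendix 1 show no eligibility check on Day 1, add a mark there so that the score is reviewed before open-label drug is started.

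The cost is the added line and the mark. No assessment is added, no analysis changes, and no patient who could have been randomized is excluded.

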9.7.3 Timed items

• Rising from floor – the time required in rising from the supine position

- Rising from a chair the time required to stand from a seated position
- Climbing 4 steps the time required to climb 4 standardized steps
- Walking 10 meters the time required to walk 10 meters as fast as possible

9.7.4 Quality of life assessment

The Individualized Quality of Life for neuromuscular disease (INQoL) or the Pediatric Quality of Life (PEDSQLTM) will be assessed for adult or pediatric patients, respectively. Each QoL evaluation is available in the local language for the appropriate sites.

10 Reporting Adverse Events

10.1 Adverse Events

For this protocol, a reportable AE is any untoward medical occurrence (e.g. sign, symptom, illness, disease or injury) in a patient administered the IP or other protocol-imposed intervention, regardless of attribution. This includes:

- AEs not previously observed in the patient that emerge during the study.
- Pre-existing medical conditions judged by the Investigator to have worsened in severity or frequency or changed in character during the study.
- Complications that occur as a result of non-drug protocol-imposed interventions.

An adverse drug reaction is any AE for which there is a reasonable possibility that the IP caused the AE. "Reasonable possibility" means there is evidence to suggest a causal relationship between the IP and the AE.

Whenever possible, it is preferable to record a diagnosis as the AE term rather than a series of terms relating to a diagnosis.

The study period during which all non-serious AEs will be reported begins after the first administration of study drug through the termination visit or at the early termination visit. After informed consent but prior to initiation of study treatment, only SAEs associated with any protocol-imposed interventions will be reported. The criteria for determining, and the reporting of SAEs is provided in Section 10.2 Serious Adverse Events

The Investigator should follow all unresolved AEs until the events are resolved or stabilized, the patient is lost to follow-up, or it has been determined that the study treatment or participation is not the cause of the AE. Resolution of AEs (with dates) should be documented on the appropriate CRF page(s) and in the patient's medical record.

The Investigator responsible for the care of the patient or qualified designee will assess AEs for severity, relationship to IP, and seriousness (refer to Section 10.2 Serious Adverse Events for SAE definition). Severity (as in mild, moderate or severe headache) is not equivalent to seriousness, which is based on patient/event outcome or action criteria usually associated with events that pose a threat to a patient's life or functioning. Seriousness (not severity) serves as a guide for defining regulatory reporting obligations.

The Investigator will determine the severity of each AE using grades defined in Table 5 Categories of Severity for Adverse Events (the event will be recorded on the source documents and AE CRF). Events that are Grades 4 and 5 are serious events and require completion of both an SAE form and AE CRF.

Table 5 Categories of Severity for Adverse Events

Severity	Description					
Grade 1	Mild; asymptomatic or mild symptoms; clinical or diagnostic observations only; intervention not indicated.					
Grade 2	Moderate; minimal, local or noninvasive in limiting age-appropriate instrumental ADL	ź				
Grade 3	Severe or medically significant but not immediately life-threatening; hospitalization or prolongation of hospitalization indicated; disabling; limiting self-care ADL**.					
Grade 4	Life-threatening consequences; urgent intervention indicated.	Note: Grade 4 and 5 adverse events should				
Grade 5	Death related to AE.	always be reported as serious adverse events				

Activities of Daily Living (ADL)

The Investigator will suggest the relationship of an AE to the IP and will record it on the source documents and AE CRF, using the relationship categories defined in Table 6.

^{*} Instrumental ADLs refer to preparing meals, shopping for groceries or clothes, using the telephone, managing money, etc.

^{**}Self-care ADLs refer to bathing, dressing and undressing, feeding self, using the toilet, taking medications, and not bedridden.

Table 6 Description of Relationship to Adverse Event Categories

Relationship Category	Description
Not Related	Exposure to the IP has not occurred OR The administration of the IP and the occurrence of the AE
	ore not reasonably related in time OR The AE is considered likely to be related to an etiology other
	than the use of the IP; that is, there are no facts [evidence] or arguments to suggest a causal relationship to the IP.
Possibly Related	The administration of the IP and the occurrence of the AE are reasonably related in time AND
	The AE could be explained equally well by factors or causes other than exposure to the IP.
Probably Related	The administration of IP and the occurrence of the AE are reasonably related in time AND
	The AE is more likely explained by exposure to the IP than by other factors or causes.

In order to classify AEs and diseases, preferred terms will be assigned by the sponsor to the original terms entered in the CRF, using Medical Dictionary for Regulatory Activities (MedDRA) terminology.

